4.2. Primary Endpoint(s) Analyses

Primary estimands (refer Section 1.1) for primary endpoints will be implemented for the primary analysis. Primary endpoint analysis will be based on MCC analysis set.

4.2.1. Definition of endpoints

The Primary endpoints are defined in Section 1.1.

The definitions of MCC parameters are described in the following table:

Table 1 MCC parameters

Parameter	Description
AUC0-4h (primary)	Area under the right lung percent radiolabeled particle retention -time curve up to 4 h after dosing with ^{99m}Tc on Day 7
R1h (secondary)	Right lung percent radiolabeled particle retention at 1 h after dosing with ^{99m}Tc on Day 7
R1.5h (secondary)	Right lung percent radiolabeled particle retention at 1.5 h after dosing with ^{99m}Tc on Day 7
R3h (secondary)	Right lung percent radiolabeled particle retention at 3 h after dosing with ^{99m}Tc on Day 7

4.2.2. Main analytical approach

The primary MCC endpoint will be analysed using MCC analysis set.

For the \log_e transformed data of AUC(0-4h), descriptive statistics (N, n, GM, 95% CI of GM, SD (\log_e), between- subject coefficient of variation [CV_b in %]) will be presented, where $\%CV_b = 100 * (\text{SQRT}(\text{EXP}(\text{SD}^2) - 1))$ and SD is the standard deviation on the \log_e scale.

For the untransformed data of AUC(0-4h), descriptive statistics (N, n, AM, 95% CI of AM, SD median, minimum and maximum) will be computed.

Following \log_e -transformation, AUC(0-4h) will be analyzed using mixed effect model approach with fixed effect terms for period and treatment group. Participants will be treated as random effects in the model. Unstructured (UN) variance and covariance structures will be assumed. If the above model fails to converge, other covariance structures (e.g. CS, AR(1) etc.) might be investigated. The point estimates and their associated 90% CI will then be back-transformed to provide point estimates and 90% CI for the ratios (GMR) of HFA-152a (test)/HFA-134a (reference).

If an intercurrent event (ICE) (as described in Section 1.1) happens during a specific treatment period, and this event affects the measurement of individual MCC data, then the data points for those affected individuals in the treatment period will not be used for the analysis.

In cases where the measurement is not performed, it will be treated as missing data.

Graphs for MCC parameters -

- Individual percent radiolabeled particle retention - time plots (linear and semi-logarithmic) by subjects
- Individual percent radiolabeled particle retention - time plots (linear and semi-logarithmic) by treatment group
- Median (range) percent radiolabeled particle retention - time plot (linear and semi-logarithmic) by treatment group
- Mean (+ SD) percent radiolabeled particle retention - time plots (linear and semi-logarithmic) by treatment group
- Percent radiolabeled particle retention – time (box plots) by treatment group

Listing for primary endpoint will be generated using MCC analysis set.

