4. STUDY DESIGN

4.1. Overall Design

This is a randomized, double-blind, single-site, 2-way crossover study to assess the effect of repeated doses of Test propellant (HFA-152a, aka 1 – Difluoroethane) on MCC as compared to Reference propellant (HFA-134a, aka 1,1,1,2 – Tetrafluoroethane) in healthy male and female participants.

The study has planned to enrol a total of 24 healthy participants to ensure at least 20 participants are included in the principal stratum analysis set with at least 10 participants randomized to each treatment sequence.

Participants will be randomly assigned to 1 of 2 treatment sequences in 2 TPs using a cross-over design. The following treatment sequences will be tested:

- Treatment Sequence 1: T-R
- Treatment Sequence 2: R-T

[figure not shown]
Where T is HFA-152a, aka 1 – Difluoroethane (Test) and R is HFA-134a, aka 1,1,1,2 – Tetrafluoroethane (Reference).

In each study period, Test or Reference propellants will be administered by oral inhalation BID on Days 1-6 and as a single dose on the morning of Day 7. MCC will be determined using gamma-scintigraphy following the administration of nebulized colloidal ^{99m}Tc-sulphur colloid by inhalation after the final dose of the propellant on Day 7. The

study will comprise a Screening Period of up to 21 days prior to first dosing; 2 TPs of 8 days each, with a 7 ± 2 days Washout Period between the 2 TPs; and a final safety Follow-up Visit up to 8 ± 2 days after the final dose administration in TP2 (maximal duration 56 days).

A schema of the study is provided in Figure 1.

Figure 1 Schematic of the Study

Notes: Training MDI concerns the initial training of the inhalation from MDI (propellants); additional training will be provided during the treatment periods. Between Day 1 to Day 6 of Period 1, the ROI encompassing the right lung will be defined based on a single ^{57}Co transmission scan of the participant chest. Green triangles represent propellant administrations (4 inhalations BID for 6 days + single morning administration on Day 7). Tc Training inhalation concerns the training of inhalation of nebulized saline solution (without radiolabeled $^{99\text{m}}\text{Tc}$); Yellow boxes represent inhalation of the nebulized labelled $^{99\text{m}}\text{Tc}$ for the assessment of MCC.

Abbreviations: BID=twice daily, Co=Cobalt, MDI=metered dose inhaler, ROI=region of interest, Tc=Technetium.

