4.4. End-of-Study Definition

A participant is considered to have completed the study if the participant has completed the 2 treatment periods of the study including the last visit or the last scheduled procedure shown in the SoA (see Section 1.3).

The end of the study is defined as the date of the last visit of the last participant in the study or last scheduled procedure shown in the SoA for the last participant in the study. The Ethics Committee should be notified of the conclusion of the study within 90 days of the end of the study, or within 15 days if the study is terminated early, clearly explaining the reasons for the termination. The ARSAC Practitioner will also be notified of the end of trial or early termination of the trial within an appropriate timeframe.

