7. DISCONTINUATION OF STUDY INTERVENTION AND PARTICIPANT DISCONTINUATION/WITHDRAWAL

7.1. Discontinuation of Study Intervention

Discontinuation of study intervention refers to any participant who has not received all planned sequences of the study intervention. In rare instances, it may be necessary for a participant to permanently discontinue study intervention. If study intervention is permanently discontinued in a particular period, all reasonable attempts will be made to ensure the collection of endpoints and safety information (e.g., telephone contact) in that period and follow-up.

[figure not shown]
See the SoA for data to be collected at the time of discontinuation of study intervention and follow-up and for any further evaluations that need to be completed. The primary reason for premature discontinuation of the study intervention will be documented in the eCRF based on the list below:

Reason	Additional Items/Sub-reasons
AE	
Lost to follow-up	Participant relocated Participant was incarcerated Other, specify Unknown
Participant achieved protocol-defined stopping criteria	Liver chemistry stopping criteria QTc stopping criteria Bronchospasm stopping criteria
Physician decision	Specify
Protocol deviation	Specify
Site terminated by the Sponsor	
Study treatment terminated by the Sponsor	
Study terminated by the Sponsor	
Withdrawal by participant	Burden of procedure Participant relocated COVID-19 pandemic Other, specify
Other	Specify
Death	

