9.2. Analysis Sets

Analysis Set	Definition / Criteria	Analyses Evaluated
Screened	
 All participants who were screened for eligibility. 	
 All Screened, Reason for Screen Failures
Enrolled	
 All participants who screen passed and entered in the study (who were randomized). Note screening failures (who never passed screening even if rescreened) and participants screened but never enrolled into the study (met eligibility but not needed) are excluded from the enrolled analysis set 	
 Study Population

Analysis Set	Definition / Criteria	Analyses Evaluated
	as they did not enter the study.	
MCC (Principal Stratum)	
 All participants who were able to adhere to all doses of study intervention as prescribed and completed the study 	
 Estimand for primary and secondary objective of MCC parameters
Safety	
 All participants who received at least one dose of study intervention. 	
 Estimand for secondary safety objective

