9.3.1.4. Supplementary/supportive Analysis

No supplementary/supportive analysis will be performed.

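### The MCC analysis set and SAP 4.2.2 set different exclusion rules for the primary analysis, and set membership depends on a safety visit held after all imaging

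*SAP*

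**What the plan says.** Protocol 9.2 defines the MCC (principal stratum) set as "All participants who were able to adhere to all doses of study intervention as prescribed and completed the study". SAP 3 repeats this. The estimand text in Protocol 3 and SAP 1.1 describes the same kind of person, a completer who is fully compliant and has no dosing error. It lists three intercurrent events (ICEs): treatment discontinuation, not taking all doses, and dosing error. Protocol 9.3.1.2 refers back to Protocol 3 for how ICEs are handled.

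SAP 4.2.2 opens by naming the MCC set as the analysis population. It then adds a rule for one of those ICEs in a specific period: if "this event affects the measurement of individual MCC data, then the data points for those affected individuals in the treatment period will not be used". SAP 4.3.1.2 applies the same handling to the secondary MCC endpoints. SAP 4.8 declares one change from the protocol, the added Full Analysis Set; the period-level rule is not mentioned.

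The SAP does not define study completion. Protocol 4.4 does: a participant must have "completed the 2 treatment periods of the study including the last visit or the last scheduled procedure shown in the SoA". In the schedule of activities the last column is the follow-up, which Protocol 4.1 calls the "final safety Follow-up Visit".

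Protocol 7.1 says that after discontinuation "all reasonable attempts will be made to ensure the collection of endpoints and safety information". Protocol 9.3.1.4 states "No supplementary/supportive analysis will be performed", and SAP 4.2.2 states "Listing for primary endpoint will be generated using MCC analysis set".

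**The concern.** The set works on whole participants and has no exceptions. The 4.2.2 sentence works on single periods and is conditional. It presupposes that people with an ICE are in the analysis, keeps their other period, and keeps both periods if the event is judged harmless. No document says who makes that judgement, by what criterion, or whether it precedes sight of the MCC data. Participants are random effects in the model, so single-period data can enter the fit. Two programmers following the SAP in good faith could therefore produce different primary GMRs.

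The completion wording is a separate problem in the same rule. Follow-up attendance after Period 2 cannot change a Day 7 scan already acquired, and a missed follow-up is not a listed ICE. Yet on the protocol's only definition of completion it removes the participant from the primary and secondary MCC analyses.

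**Working it through.** **1. The plan's own figure.** Inputs from SAP 5 (Protocol 9.5): n = 20 in the MCC set, CVw 10.5% (log SD 0.1047), two-sided 90% CI. For a balanced 2×2 crossover,

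half-width = exp[t(0.95, n−2) × SDw × √(2/n)] − 1.

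With t(0.95, 18) = 1.734: 1.734 × 0.1047 × √(2/20) = 0.0574, and exp(0.0574) − 1 = 5.91%. The plan states 5.93%. All 16 cells of SAP Table 3 reproduce within 0.025 percentage points, so the formula is a fair basis for comparison.

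**2. The two rules side by side.**

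| Case | MCC set | 4.2.2 sentence on its own | Set first, then 4.2.2 |
|---|---|---|---|
| One missed dose in Period 1, judged not to affect MCC | Both periods out | Both periods in | Both out; sentence idle |
| Same missed dose, judged to affect MCC | Both periods out | Period 1 out, Period 2 in | Both out; sentence idle |
| Dosing error in one period | Unclear: the estimand names it, the set definition does not | That period out only if judged to affect MCC | Sentence may decide |
| All doses taken, two valid scans, follow-up missed | Both out under Protocol 4.4 | Both in (not an ICE) | Both out |

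The first two rows differ between rules. The third is the only place where the sentence could do work within the set. The fourth follows from Protocol 4.4. The alternative it offers between last visit and last scheduled procedure does not help, because the last scheduled procedures are also at the follow-up visit.

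**3. Size.** Take 24 randomized with 4 affected, as an illustration; the documents give no expected number. SDw = 0.1047.

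- Whole-participant rule, 20 pairs: 5.91%, as above.
- Period-level rule, event judged to affect the measurement, 20 pairs plus 4 single periods: 5.68% to 5.88%. This is generalized least squares with a random participant intercept, period and treatment fixed, and 18 df. The assumed between-subject log SD runs from 0.05 to 0.30 and is not in the documents.
- All 24 kept (event judged harmless, or only the follow-up missed): t(0.95, 22) = 1.717; 1.717 × 0.1047 × √(2/24) = 0.0519; exp(0.0519) − 1 = 5.33%.

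The whole range is 5.91 − 5.33 = 0.58 percentage points.

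**The case against.** The strongest reply is that the two rules run in sequence: the set fixes the population and the ICE sentence is a second filter inside it. On that reading they do not strictly contradict each other, and a reader who infers that both cannot hold goes too far. What stands is that this reading leaves the sentence with nothing to do except possibly for dosing errors. Its wording still invites a programmer to apply it more widely.

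SAP 6.1.3 plans a pre-freeze review of deviations that lead to exclusion from analysis populations, and the study is double-blind. That largely covers set membership. It does not expressly cover the period-level judgement.

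On completion, Protocol 7.3 asks the site to reschedule missed visits, so one missed appointment need not mean non-completion. The SAP also does not cite Protocol 4.4. The exclusion is what the text implies, not a certain outcome.

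A reader might also infer that the target of 20 in the set is at risk. Full compliance spans 13 × 2 = 26 administrations. At an assumed 0.5% deviation rate, independent across doses, 0.995^26 = 0.878, and the chance of at least 20 of 24 is 0.84; at 0.2% it is 0.99. If 5% also missed follow-up, these fall to 0.63 and 0.92. The documents give none of these rates. Dosing is given by site staff under supervision (Protocol 6.5) during confinement. Any sound all-doses rule would leave the 0.84 unchanged; only the follow-up part can be recovered.

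Nor do the documents support saying that participants who stop disappear from the results. Protocol 7.2 says data up to withdrawal enter the study analyses, SAP 4.1.1 plans MCC summaries and listings without naming a set, and adverse events are reported in the Safety set. The narrower point that stands is that no MCC analysis or primary-endpoint listing is named for them.

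**Conclusion.** The exclusion rules are wrong as written and should be fixed; this is not a must-fix. The set and SAP 4.2.2 do not describe one analysis. The 4.2.2 judgement has no criterion or blinded timing, and the completion wording can discard valid paired scans for a reason unrelated to mucociliary clearance.

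The precision effect is small: 5.91% against 5.33% with 4 of 24 affected at CVw 10.5%. The main consequence is which participants and periods determine the GMR. How much the estimate itself could move cannot be computed, because the documents give neither an ICE rate nor the outcomes of those affected. With no ICE and full follow-up attendance the rules coincide. The study is descriptive, with no hypothesis test and no stated acceptance margin, which also limits the severity.

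The follow-up point assumes that completion in the set definition carries the meaning in Protocol 4.4, the only definition given.

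**What to change.** - Define the MCC set, in Protocol 9.2 and SAP 3, as participants who took all doses as prescribed with no dosing error in both treatment periods, regardless of attendance at the safety follow-up. Align the completion wording in the estimand text (Protocol 3, SAP 1.1).
- Delete the period-level ICE sentence from SAP 4.2.2. SAP 4.3.1.2 then follows automatically.
- State in SAP 6.1.3 that membership is fixed blind to treatment and before MCC results are reviewed, within the pre-freeze review already planned.
- Do not make an evaluable AUC(0-4h) in both periods a condition of membership. That would select on the outcome being observed, discard single-period data the mixed model can use, and undercut the sensitivity analysis planned for more than 10% missing data (Protocol 9.3.1.3, SAP 4.2.3). Leave missing AUC to the model and that analysis.
- Optionally, list MCC data for everyone with any Day 7 scan, consistent with Protocol 7.2. A further supplementary model is a matter of preference.

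Cost: SAP wording and a small protocol clarification, plus one listing if wanted. No extra participants or procedures.

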4.2.3. Sensitivity analyses

If missing data is more than 10% then a sensitivity analysis will be conducted by using AUC0-4h estimated by linear extrapolation method of the log-transformed data.

The same analytical method (as described in Section 4.2.2) will be used with the AUC0-4h estimated data.

4.2.4. Additional estimands

Not Applicable.

4.3. Secondary Endpoint(s) Analyses

Secondary MCC endpoints will be analysed using the secondary estimand (refer to Section 1.1). Secondary endpoint analysis will be based on MCC analysis set.

4.3.1. Secondary MCC endpoints

The secondary MCC endpoints are as follows:

- Right lung percent radiolabeled particle retention at 1 h after dosing with ^{99m}Tc on day 7
- Right lung percent radiolabeled particle retention at 1.5 h after dosing with ^{99m}Tc on day 7
- Right lung percent radiolabeled particle retention at 3 h after dosing with ^{99m}Tc on day 7

4.3.1.1. Definition of secondary MCC endpoints

For the definitions of secondary MCC parameters, refer Section [4.2.1](#).

4.3.1.2. Main analytical approach

For the untransformed secondary endpoints data, descriptive statistics (N, n, AM, 95% CI of AM, SD) median, minimum and maximum) will be computed.

Secondary endpoints will be analyzed using mixed effect model approach with fixed effect such as period, treatment group and participants as random effects. The point estimates of mean difference and their associated 90% CI will be provided for HFA-152a (Test) and HFA-134a (Reference).

ICEs will be managed in the same way as primary endpoint.

4.3.1.3. Sensitivity analyses

If the distribution of the secondary endpoints' (percent radiolabeled particle retention at 1, 1.5, 3 h after dosing with ^{99m}Tc on day 7) data does not follow normal distribution, then loge transformation will be applied.

Loge transformed data of secondary endpoints will be analyzed using mixed effect model approach with fixed effect such as period, treatment group and participants as random effects. The point estimates and their associated 90% CI will then be back-transformed to provide point estimates and 90% CI for the ratio (GMR) of HFA-152a (Test) / HFA-134a (Reference).

If missing data of percent radiolabeled particle retention at either timepoint (1h, 1.5h and 3h) is > 10% then sensitivity analysis will be performed using data obtained using log-linear interpolation/extrapolation imputation of available measurements

4.3.1.4. Additional estimands

Not applicable

4.3.2. Supportive secondary endpoint(s)

Not applicable.

4.4. Tertiary/Exploratory Endpoint(s) Analyses

Not applicable.

4.5. Safety Analyses

Safety analysis set will be used for the analysis of safety endpoints. Secondary estimand to analyses safety endpoints (refer Section 1.1) will be implemented. No formal statistical comparisons will be made for safety data. All safety data will be reported according to the actual treatment the subject received.

The tables will use the “safety” population unless otherwise specified.

4.5.1. Extent of Exposure

The total exposure on study (propellant HFA-152a (Test) or HFA-134a MDI (Reference)) is calculated as the date of last dose of study treatment minus first dose of study treatment plus one. Subjects who entered the study treatment phase but did not report any treatment dates will be categorized as having zero days of exposure. For each treatment and period, dose administration and exposure data for all participants will be generated in the listing for MCC.

4.5.2. Adverse Events

The applicable definition of an AE and SAE are in the study protocol Sections 8.4 and 10.3. All reported AEs will be coded using the standard GSK dictionary, (MedDRA ≥ 26.1 version).

An AE is considered study treatment emergent (on-treatment) if the AE onset date is on or after study treatment start date and on or before study treatment stop date plus 1 day (inclusive) follow-up or worsens (change in AE severity from lower severity to higher severity category) relative to the pre-study treatment state.

AEs occurring following dosing in a specific period but before dosing in the next period will be attributed to that specific period. If the time is missing for an AE on a dosing day then the AE will be attributed to the treatment given on that day.

Overview of AEs:

The following points will be presented in a summary table for overview of AEs in overall (on and post-treatment) and on-treatment period.

- Total number of AEs reported with the number of participants who experienced at least 1 AE
- AE by maximum severity intensity

- Drug-related AE and SAE, fatal SAE, drug-related fatal SAE, non-fatal SAE, drug-related non-fatal SAE
- AE leading to discontinuation of study treatment and AE leading to withdrawal from study

AEs and SAEs by SOC and PT:

The below summaries (counts and percentages) will be produced for AEs and SAEs by system organ classes (SOC) and (PT) for overall (on- and post-treatment) and on-treatment period.

- Summary of AEs by SOC and PT
- Summary of SAEs by SOC and PT
- Summary of SAEs by SOC and PT with number of subjects and occurrences

Common AEs:

The following summaries (counts and percentages) will be displayed for common ($\geq 10\%$ incidence, before rounding) AEs for overall (on- and post-treatment) and on-treatment period.

- Summary of common ($\geq 10\%$) AEs by PTs
- Summary of common ($\geq 10\%$) Non-SAEs by SOC and PTs with number of subjects and occurrences
- Summary of Non-SAEs (0-5%) by SOC and PTs with number of subjects and occurrences
- Summary of common ($\geq 10\%$) SAEs by SOC and PTs with number of subjects and occurrences

AEs and SAEs related to study treatment:

Relationship to study treatment, as indicated by the investigator, is classified as “not related” or “related”. AEs with a missing relationship to study treatment will be recorded as “related” to study treatment. If a participant reports the same AE more than once within an SOC/PTs, the AE with the worst-case relationship to study treatment will be used in the corresponding relationship summaries.

The following summaries (counts and percentages) will be presented for drug-related AEs and SAEs for on-treatment period

- Summary of drug-related (Propellant) AEs by overall frequency (SOC and PT), by test /reference propellant.
- Summary of drug-related (Propellant) SAEs by overall frequency (SOC and PT), by test /reference propellant.
- Summary of serious fatal and non-fatal drug-related adverse events (Propellant) will be created by overall frequency (SOC and PT), by test /reference propellant.

- Summary of drug-related (Propellant) non-serious AEs by SOC and PT will also be presented , by test /reference propellant.
- Summary of drug-related (99mTc-sulphur colloid inhalation) AEs by overall frequency (SOC and PT)
- Summary of drug-related (99mTc-sulphur colloid inhalation) SAEs by overall frequency (SOC and PT)

AEs and SAEs by severity:

Adverse event severity is categorised as mild, moderate, severe. Adverse events starting after the first dose of study treatment with a missing severity will be classified as severe. If a participant reports an AE more than once within an SOC/PTs, the AE with the worst-case (maximum) severity will be used in the corresponding severity summaries.

The following summaries (counts and percentages) will be produced for severity of AEs and SAEs by SOC, PTs, and maximum severity in overall (on- and post-treatment) and on-treatment period.

- Summary of AEs by SOC and PT and maximum severity
- Summary of SAEs by SOC and PT and maximum severity

AEs and SAEs leading to permanent discontinuation of study treatment

The below summaries (counts and percentages) for AEs and SAEs leading to permanent discontinuation of study treatment by SOC and PTs and maximum severity will be generated in overall (on- and post-treatment) and on-treatment period.

- Summary of AEs leading to permanent discontinuation of study treatment by SOC and PT
- Summary of SAEs leading to permanent discontinuation of study treatment by SOC and PT

Adverse events analyses including the analysis of AEs and SAEs will be based on GSK Core Data Standards(IDSL).

Separate listings will be produced of all AEs for each treatment and period in FAS. Summary of death will be summarized and participants profile for death will also be listed using enrolled participants.

In summary tables, SOC will be sorted in descending order of the total incidence then alphabetically, PTs will be sorted in descending order of the total incidence then alphabetically within the SOC.

For completely missing or partial missing AE start date or end date, imputation rules will be applied following Appendix 2 Section [6.3.5](#).

Details of the planned displays for AEs and SAEs are provided in Output programming specifications (OPS) and will be based on GSK Data Standards and statistical principles.

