- Administration of nebulized 99mTc inhalation given 30 \pm 10 min after the last propellant intake. Measurement of retained radioactivity will be performed immediately after nebulized 99mTc administration (scintigraphic time="0") and then at 15, 30, 45, 60, 90, 120, 150, 180, 210, 240 min after nebulized 99mTc administration.
- All AEs will be collected from the start of study intervention until final discharge from the study (including washout period). All SAEs will be collected from the signing of the Informed consent form (ICF) until final discharge from the study (including washout period).

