2.2.1. Risk Assessment

Ventolin formulated with the Reference propellant, has been on the market for many years and, thus, has a well characterized tolerability profile. The change in propellant from HFA-134a to HFA-152a is supported by a nonclinical toxicology program for HFA-152a conducted by the propellant manufacturer in accordance with ICH guidelines. In human exposure studies, HFA-152a was well tolerated, and was rapidly cleared from the blood [Kuehl, 2022]. The Sponsor's assessment of known and potential risks of this study are summarized in Table 2. Concerning exposure to radiolabeled compounds, see Section 10.9.

^{99m}Tc sulphur colloid injection is marketed in the USA for intravenous, subcutaneous, intraperitoneal and oral administration for imaging studies. Full details on adverse reactions using the approved routes of administration can be found in the prescribing information for ^{99m}Tc sulphur colloid injection. The most frequently reported adverse reactions, across all categories of use and routes of administration, include rash, allergic reaction, urticaria, anaphylaxis/anaphylactic shock, and hypotension. Less frequently reported adverse reactions are fatal cardiopulmonary arrest, seizures, dyspnea, bronchospasm, abdominal pain, flushing, nausea, vomiting, itching, fever, chills, perspiration, numbness, and dizziness. Local injection site reactions, , have also been reported.

^{99m}Tc sulphur colloid injection can be used to identify pulmonary aspiration, therefore although it is not licensed to be administered into the lungs, this route is known to be tolerated. Additionally, the use of inhaled ^{99m}Tc sulphur colloid in 0.9% sodium chloride to assess lung MCC has been safely performed in clinical studies since the 1980s [Bennett, 2015].

Table 2 Summary of Potential Risks of Clinical Significance

Potential Risk of Clinical Significance	Summary of Data/Rationale for Risk	Mitigation Strategy
Study intervention [Test and Reference propellants and radiolabeled compound]		

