9.3.2.1. Adverse Events

All reported AEs will be coded using the standard GSK dictionary (MedDRA) and grouped by body system and preferred terms. Counts and percentages for AEs, and SAEs will be produced by system organ class and preferred terms. AEs and SAEs will also be presented for overall and on-treatment period. The number and percentages will be provided for all AEs, study treatment – related AEs, and SAEs, deaths, fatal AEs, non-fatal SAEs, and AEs leading to study treatment or study withdrawal. AEs and SAEs will be summarized by severity.

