6.3.2. Study Period

Assessments and events will be classified according to the time of occurrence relative to the study treatment period (days).

Pre-Treatment : For the presentation of serious adverse events (SAEs), concomitant medications, and other assessments in pre-treatment is defined as -

Date of assessment < Study treatment start date of period 1 (Day 1).

On-Treatment : For the presentation of adverse events (AEs), serious adverse events (SAEs), concomitant medications, 12-lead ECG, vital signs, and other assessments in on-treatment is defined as -

Study treatment start date of period 1 (Day 1 of Period 1) <= Date of assessment < Study treatment stop date of period 2 (Day 8 of Period 2) or early withdrawal + 1 days

If time of assessment or study treatment is not collected (missed), the following assessment on the first dose date will be assumed to be taken prior to the first dose and therefore considered pre-treatment .

Post-Treatment : For the presentation of adverse events (AEs), serious adverse events (SAEs), concomitant medications, 12-lead ECG, vital signs and laboratory assessments in post-treatment is defined as

Date of assessment > Study treatment stop date of period 2 (Day 8 of Period 2) or early withdrawal + 1 days.

Please refer Section 6.3.5 for handling of missing and partial dates of assessments.

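### The related-AE tables by SOC and PT stop at Period 2 Day 8, so about 5–10 days of collected follow-up are missing from the only summaries that pair event type with attribution

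*SAP*

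**What the plan says.** SAP 4.5.2 organises the AE summaries in blocks. The overview, the SOC/PT tables for all AEs and SAEs, the common-AE tables, the severity tables and the tables of events leading to discontinuation are each planned for overall (on- and post-treatment) and for on-treatment.

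The block on events related to study treatment differs. It opens with "The following summaries (counts and percentages) will be presented for drug-related AEs and SAEs for on-treatment period" and gives no overall version. That line governs six tables:
- four for propellant: AEs, SAEs, fatal and non-fatal serious events, and non-serious AEs
- two for the colloid: AEs and SAEs

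On the window, SAP 4.5.2 counts an AE as on-treatment if it starts "on or before study treatment stop date plus 1 day (inclusive) follow-up". SAP 6.3.2 requires the date to be strictly earlier than "Study treatment stop date of period 2 (Day 8 of Period 2) or early withdrawal + 1 days".

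On timing, Protocol 4.1 gives the last propellant dose of each period "as a single dose on the morning of Day 7". The Schedule of Activities (SoA) places the colloid 30 ± 10 "min after the last propellant intake". Protocol 8.4.2 collects AEs from the start of study intervention until final discharge from the study.

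Protocol 9.3.2.1 says "AEs and SAEs will also be presented for overall and on-treatment period". Its next sentence promises numbers and percentages for several categories, including treatment-related AEs, and names no window.

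**The concern.** Safety is a secondary objective, and its estimand takes all AEs and SAEs to be of interest so that reporting is complete. Two kinds of intervention are given, the propellants and the colloid, and Protocol 10.3.5.3 asks the investigator to say, where possible, which one an event is related to. The six related-event tables are the only planned summary tables that show this attribution together with the type of event.

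Restricting them to on-treatment closes them about one day after the second colloid inhalation, although AE collection continues to the follow-up visit. The Day 8 cut-off also coincides with discharge from the unit, so the outpatient time after Period 2 is what drops out. The SAP gives no reason for treating this block differently from its neighbours.

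**Working it through.** **1. The plan's own figure.** The only printed number that depends on the follow-up window is the maximal duration of 56 days (Protocol 4.1). Screening 21 + Period 1 8 + washout 9 + Period 2 8 + follow-up 10 = 56, with follow-up counted from discharge on Day 8. Counted from the final dose on Day 7, it is 21 + 8 + 9 + 7 + 10 = 55. Protocol 4.1 anchors the visit on the final dose and the SoA anchors it on discharge. The two passages need reconciling, and I carry both.

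**2. Last on-treatment day in Period 2.**
- SAP 4.5.2: last dose Day 7 + 1 day, inclusive, gives Day 8.
- SAP 6.3.2: date < Day 8 + 1 = Day 9, so the last day is again Day 8.

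**3. Follow-up days outside the related-event tables.** Uncovered days = visit day − 8. The share is taken over the days from Day 7 to the visit, counted inclusively.

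| Anchor for 8 ± 2 days | Visit day | Uncovered days | Share of Day 7 to visit |
|---|---|---|---|
| Final dose, Day 7 (Protocol 4.1) | 13 to 17 | 5 to 9 | 5/7 = 71% to 9/11 = 82% |
| Discharge, Day 8 (SoA) | 14 to 18 | 6 to 10 | 6/8 = 75% to 10/12 = 83% |

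Together this gives 5–10 days. That range is derived; the documents print only 8 ± 2 days.

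**4. What is scheduled in that time.** Protocol 5.4.1 has the Day 7 safety bloods taken before any study treatment that day. The SoA laboratory row then has no mark until follow-up. The row's footnote says discharge, which I read as final discharge because Day 8 carries no mark. On that reading, the follow-up tests are the only scheduled laboratory tests after the Period 2 colloid dose. Under Protocol 8.3.5 a clinically significant change is recorded as an AE. A colloid-related laboratory AE first found and dated there would miss both colloid tables.

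**5. Where a related event starting in follow-up would appear.**

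| Output | Included? | What it shows |
|---|---|---|
| Overview, overall column | Yes | Related count; no SOC/PT, no propellant/colloid split |
| All-causality SOC/PT tables, overall | Yes | Event type, without attribution |
| Severity tables, overall | Yes | Type and severity, without attribution |
| Listing of all AEs | Yes | Individual record |
| Six related-event tables | No | Type with propellant or colloid attribution |

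The related count in the overview's overall column therefore need not reconcile with the six tables.

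**6. Period 1.** SAP 6.3.2 runs one window from Period 1 Day 1 to the end of Period 2, and SAP 4.5.2 assigns events before the next dosing to the preceding period. Related events in the washout are then counted. SAP 4.5.2 does not say whether its stop date is per period. If it is, related events in the 7 ± 2 day washout drop out as well and the gap is larger.

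**The case against.** The strongest reply is that nothing is lost. As step 5 shows, the event is in the overview, the overall SOC/PT and severity tables, and the listing. With 24 participants, anyone comparing the overall and on-treatment tables can see which preferred term was added. This stands, and it is why the point is minor.

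A short window for related events is also a defensible convention. Protocol 4.2 relies on a very short residence of the propellant in the body, and participants stay on site for 24 hours after the colloid. Protocol 2.2.1 lists reactions to the colloid that "include rash, allergic reaction, urticaria, anaphylaxis/anaphylactic shock, and hypotension", but these come from all categories of use and routes, and no onset times are given. Late related events may be few or none, and the documents give no basis for an expected number. This stands too, but the SAP does not offer it as a reason, and an empty table for the later days would itself be informative.

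The Output programming specifications, which are not available here, may add overall versions. The SAP text does not plan them.

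**Conclusion.** The point holds as a minor gap in reporting. Six tables omit about 5–10 days of collected AE time after Period 2, which is 71–83% of the days from the second colloid dose to follow-up. This rests on the on-treatment window ending on Day 8, on both follow-up anchors being possible, and on the single continuous window of SAP 6.3.2.

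A reader might infer more in four ways that the documents do not support:
- *Late related events go unreported.* They do not; they appear in several other outputs.
- *The Test–Reference comparison is biased.* Assignment to T-R and R-T is 1:1, so about 12 of 24 participants receive each propellant second and the omission is roughly balanced. SAP 4.5 plans no formal safety comparison.
- *The SAP contradicts Protocol 9.3.2.1.* The sentence on overall and on-treatment follows the one on AEs and SAEs by SOC/PT. Related AEs come in the next sentence, without a window or an SOC/PT requirement, and the overview table arguably satisfies it.
- *The window runs to Day 9.* That results only from joining the Day 8 label in SAP 6.3.2 to the inclusive rule in SAP 4.5.2. Each definition taken alone ends on Day 8.

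**What to change.** In SAP 4.5.2, extend the sentence that introduces the related-event tables so that it names both the overall (on- and post-treatment) period and the on-treatment period, as the neighbouring blocks do. If the restriction is intended, state the reason there instead.

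Two small clarifications would help the change work as meant. First, say whether the stop date in SAP 4.5.2 is per period or the end of Period 2. Second, settle the boundary day in SAP 6.3.2: on-treatment is before Day 9 and post-treatment is after Day 9, so an event dated Day 9 falls in neither. With these, uncovered follow-up after Period 2 falls to zero.

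The cost is one sentence, two clarifications and six repeat table runs on data already collected. Splitting the two colloid tables by Test and Reference propellant is optional and does not affect this point.
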